5.8.2. Biological samples

The different biological samples collected in the study, the quantity needed, the unit and the time points are described in [Table 10](#).

Table 10 Biological samples

Sample type	Quantity	Unit	Timepoint Co-Ad group	Timepoint Control group
Whole blood	Approximately 8	mL	Visit Day 1 Visit Month 1 Visit Month 3	Visit Day 1 Visit Month 1 Visit Month 2 Visit Month 5

5.8.3. Laboratory assays

Please refer to [APPENDIX A](#) for a detailed description of the assays performed in the study. Please refer to [APPENDIX B](#) for the address of the clinical laboratories used for sample analysis.

Serological assays for the determination of anti-gE antibodies will be performed by enzyme-linked immunosorbent assay (ELISA) at a GSK Biologicals' laboratory. Serological assays for the determination of pneumococcal serotype antibodies will be performed by multiplex opsonophagocytosis assay (MOPA) at a laboratory designated by GSK Biologicals using standardized and validated procedures (refer to [Table 11](#)).

(Amended 30 January 2018)

CONFIDENTIAL

204487 (ZOSTER-059 PRI)
Protocol Amendment 2 Final**Table 11 Humoral Immunity (Antibody determination)**

System	Component	Method	Unit	Cut-off	Laboratory
Serum	Varicella Zoster Virus Glycoprotein E Ab IgG	ELISA	mlU/mL	97	GSK Biologicals*
Serum	Streptococcus pneumoniae Serotype 01/37 Brugmann Hospital Ab	MOPA	1/dilution	14	University of Alabama at Birmingham**
	Streptococcus pneumoniae Serotype 03/1 Statens Serum Institut Ab			10	
	Streptococcus pneumoniae Serotype 04/2656 Brugmann Hospital Ab			41	
	Streptococcus pneumoniae Serotype 05 Ambrose- Statens Serum Institut Ab			11	
	Streptococcus pneumoniae Serotype 06A Centers for Disease Control Ab			15	
	Streptococcus pneumoniae Serotype 06B/DS2212/94 Centers for Disease Control Ab			29	
	Streptococcus pneumoniae Serotype 07F/46 Brugmann Hospital Ab			28	
	Streptococcus pneumoniae Serotype 09V/112 161/95 Statens Serum Institut Ab			14	
	Streptococcus pneumoniae Serotype 14/58 Brugmann Hospital Ab			14	
	Streptococcus pneumoniae Serotype 18C/4593/40 Statens Serum Institut Ab			26	
	Streptococcus pneumoniae Serotype 19A/DB18 Kansanterveyslaitos Folkhalsainstitutet Ab			13	
	Streptococcus pneumoniae Serotype 19F/2737 Brugmann Hospital Ab			15	
Streptococcus pneumoniae Serotype 23F Mac- Statens Serum Institut Ab	22				

*GSK Biologicals laboratory refers to the Clinical Laboratory Sciences (CLS) in Rixensart, Belgium; Wavre, Belgium.

**Pathology Department of Professor, [name], WHO Pneumococcal Serology Reference Laboratory, The University of Alabama at Birmingham, [name]

MOPA: multiplex opsonophagocytosis assay; ELISA: enzyme-linked immunosorbent assay; Ab: antibody; IgG: immunoglobulin G; *S pneumoniae*: *Streptococcus pneumoniae*.

Additional exploratory testing on the vaccine and/or on the disease under study may be performed within the framework of the study if deemed necessary for accurate interpretation of the data or should such assay(s) become available at GSK. These assays may not be represented in the objectives/endpoints of the study protocol.

The GSK Biologicals' / **contract research organizations' (CRO)** clinical laboratories have established a Quality System supported by procedures. The activities of GSK Biologicals' / **CROs'** clinical laboratories are audited regularly for quality assessment by an internal (sponsor-dependent) but laboratory-independent Quality Department. ***Clinical laboratories contracted by GSK also conform to Good Laboratory Practice guidelines and operate in compliance with regulatory standards.***

(Amended 30 January 2018)

CONFIDENTIAL

204487 (ZOSTER-059 PRI)
Protocol Amendment 2 Final**5.8.4. Biological samples evaluation****5.8.4.1. Immunological read-outs**

The plan for immunogenicity testing on samples obtained is shown in [Table 12](#) and [Table 13](#) for Co-Ad and Control groups, respectively.

Table 12 Immunological read-outs for Co-Ad group

Blood sampling timepoint		No. subjects	Component
Type of contact and timepoint	Sampling timepoint		
Visit Day 1 ¹	Prevenar13 pre-vaccination	456	S pneumoniae 01 Ab
			S pneumoniae 03 Ab
			S pneumoniae 04 Ab
			S pneumoniae 05 Ab
			S pneumoniae 06A Ab
			S pneumoniae 06B Ab
			S pneumoniae 07F Ab
			S pneumoniae 09V Ab
			S pneumoniae 14 Ab
			S pneumoniae 18C Ab
			S pneumoniae 19A Ab
			S pneumoniae 19F Ab
			S pneumoniae 23F Ab
		HZ/su pre-vaccination	456
Visit Month 1	Prevenar13 post-vaccination	456	S pneumoniae 01 Ab
			S pneumoniae 03 Ab
			S pneumoniae 04 Ab
			S pneumoniae 05 Ab
			S pneumoniae 06A Ab
			S pneumoniae 06B Ab
			S pneumoniae 07F Ab
			S pneumoniae 09V Ab
			S pneumoniae 14 Ab
			S pneumoniae 18C Ab
			S pneumoniae 19A Ab
			S pneumoniae 19F Ab
S pneumoniae 23F Ab			
Visit Month 3	HZ/su post-vaccination	456	VZV Glycoprotein E Ab IgG

Ab: antibody; IgG: immunoglobulin G; *S pneumoniae*: *Streptococcus pneumoniae*; VZV: Varicella Zoster Virus.

¹ In case of inadequate samples from Visit Day 1, anti-gE testing (ELISA) will be prioritized over testing for pneumococcal serotype antibodies (MOPA).

CONFIDENTIAL

204487 (ZOSTER-059 PRI)
Protocol Amendment 2 Final**Table 13 Immunological read-outs for Control group**

Blood sampling timepoint		No. subjects	Component
Type of contact and timepoint	Sampling timepoint		
Visit Day 1	Prevenar13 pre-vaccination	456	S pneumoniae 01 Ab
			S pneumoniae 03 Ab
			S pneumoniae 04 Ab
			S pneumoniae 05 Ab
			S pneumoniae 06A Ab
			S pneumoniae 06B Ab
			S pneumoniae 07F Ab
			S pneumoniae 09V Ab
			S pneumoniae 14 Ab
			S pneumoniae 18C Ab
			S pneumoniae 19A Ab
			S pneumoniae 19F Ab
S pneumoniae 23F Ab			
Visit Month 1	Prevenar13 post-vaccination	456	S pneumoniae 01 Ab
			S pneumoniae 03 Ab
			S pneumoniae 04 Ab
			S pneumoniae 05 Ab
			S pneumoniae 06A Ab
			S pneumoniae 06B Ab
			S pneumoniae 07F Ab
			S pneumoniae 09V Ab
			S pneumoniae 14 Ab
			S pneumoniae 18C Ab
			S pneumoniae 19A Ab
			S pneumoniae 19F Ab
S pneumoniae 23F Ab			
Visit Month 2	HZ/su pre-vacc	456	VZV Glycoprotein E Ab IgG
Visit Month 5	HZ/su post-vacc	456	VZV Glycoprotein E Ab IgG

Ab: antibody; IgG: immunoglobulin G; *S pneumoniae*: *Streptococcus pneumoniae*; VZV: Varicella Zoster Virus

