The global power to meet all co-primary objectives with 410 evaluable subjects in Co-Ad and Control groups is approximately 91% (Table 23). Assuming that about 10% of the subjects enrolled are non-evaluable (e.g. due to dropout, bad sample), approximately 912 subjects will need to be enrolled (456 subjects in each treatment group).

CONFIDENTIAL

204487 (ZOSTER-059 PRI)
Protocol Amendment 2 Final**Table 23 Power to demonstrate VRR objective and non-inferiority of the immunogenicity of HZ/su and *Prevenar13* co-administered compared to Control group**

Family 1: HZ/su: VVR*(1-sided test with alpha = 2.5%)				
Endpoint	Threshold	VR assumed	Total β	Power
VRR in Co-Ad group	0.60	95%	0.001%	99.99%
Family 2: HZ/su: non-inferiority* (1-sided test with alpha = 2.5%) N=410				
Endpoint	Standard deviation	δ	Total β	Power
Anti-gE GMC ratio	0.35	1.5	0.001 %	99.99 %
Family 3: Prevenar13: Non-inferiority* (1-sided test with alpha = 2.5%) N=410				
Endpoint (13 vaccine pneumococcal serotypes)	Standard deviation	δ	Total β	Power
3 GMT ratio	0.660	2	0.001%	99.99%
19A GMT ratio	0.644	2	0.001%	99.99%
1 GMT ratio	0.798	2	0.029%	99.97%
18C GMT ratio	0.891	2	0.203%	99.80%
4 GMT ratio	0.906	2	0.260%	99.74%
6A GMT ratio	0.919	2	0.320%	99.68%
5 GMT ratio	0.931	2	0.383%	99.62%
19F GMT ratio	0.971	2	0.664%	99.33%
6B GMT ratio	0.995	2	0.891%	99.11%
7F GMT ratio	1.014	2	1.107%	98.89%
9V GMT ratio	1.021	2	1.194%	98.81%
14 GMT ratio	1.045	2	1.530%	98.47%
23F GMT ratio	1.094	2	2.398%	97.60%
Global β to show non-inferiority			~9%	
Global power				~91%

VRR: vaccine response rate; gE: Varicella Zoster Virus glycoprotein E; GMT: geometric mean titer; GMC: geometric mean concentration.

* Pass 12, alpha = 2.5%, for VRR: Exact test, for non-inferiority one-sided equivalence of means.

For gE: non-inferiority limit = 0.176 (=log₁₀(1.5)), power under equal GMC

For each pneumococcal serotype: non-inferiority limit = 0.301 (=log₁₀(2)), variability for each of the 13 vaccine pneumococcal serotype taken from the EMA assessment report for *Prevenar13* and multiplied by 1.1, power under equal GMT.

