10.9. Interpretation of analyses

All co-primary objectives will be evaluated using a one-sided Type I error of 2.5% (as already justified by fixed sequential testing procedure, no alpha adjustment needed). The trial will be considered conclusive if all co-primary objectives criteria are met.

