12.1.2. Immunogenicity

- For a given subject and given immunogenicity measurement, missing or nonevaluable measurements will not be replaced. Therefore, an analysis will exclude subjects with missing or non-evaluable measurements.
- A seronegative subject is a subject whose antibodies concentration/titer is below the cut-off value (cut-off value is defined by the laboratory prior to the analysis).
- A seropositive subject is a subject whose antibodies concentration/titer is greater than or equal to the assay cut-off value.
- The seropositivity rate is defined as the percentage of seropositive subjects.
- The VRR for anti-gE is defined as the percentage of subjects who have at least:
 - a 4-fold increase in the anti-gE antibodies concentration as compared to the prevaccination anti-gE antibodies concentration, for subjects who are seropositive at baseline, or,
 - a 4-fold increase in the anti-gE antibodies concentration as compared to the anti-gE antibodies cut-off value for seropositivity, for subjects who are seronegative at baseline.
- The GMC calculations for anti-gE antibody concentration are performed by taking the anti-log of the mean of the log base 10 concentration transformations. Antibody concentrations below the cut-off of the assay will be given an arbitrary value equal to half the cut-off for the purpose of GMC/GMT calculation.
- All CI computed will be two-sided 95% CI.

204487 (ZOSTER-059 PRI) Statistical Analysis Plan Amendment 3

• Updated LLOQ and ULOQ values for the MOPA assay are described below for each of the 13 pneumococcal serotypes:

Pneumococcal serotype	Method	Unit	LLOQ1	ULOQ	Laboratory
Streptococcus pneumoniae Serotype 01/37 Brugmann Hospital Ab			14	3504	
Streptococcus pneumoniae Serotype 03/1 Statens Serum Institut Ab			11	2822	
Streptococcus pneumoniae Serotype 04/2656 Brugmann Hospital Ab			40	18042	
Streptococcus pneumoniae Serotype 05 Ambrose- Statens Serum Institut Ab			15	13304	
Streptococcus pneumoniae Serotype 06A Centers for Disease Control Ab			45	15305	
Streptococcus pneumoniae Serotype 06B/DS2212/94 Centers for Disease Control Ab			29	20806	University of
Streptococcus pneumoniae Serotype 07F/46 Brugmann Hospital Ab	MOPA	1/ dilution	28	59809	University of Alabama at
Streptococcus pneumoniae Serotype 09V/112 161/95 Statens Serum Institut Ab			39	28095	Birmingham
Streptococcus pneumoniae Serotype 14/58 Brugmann Hospital Ab			16	47856	

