Control = Dose 1: Prevenar 13, Dose 2: HZ/su, Dose 3: HZ/su

Adjusted GMC = geometric mean antibody concentration adjusted for vaccine group, age and baseline concentration N = number of subjects with both pre- and post-vaccination results available

95% CI* = 95% confidence interval for the adjusted GMC (Ancova model: adjustment for vaccine group, age and baseline concentration - pooled variance); LL = lower limit, UL = upper limit

95% CI = 95% confidence interval for the adjusted GMC ratio (Ancova model: adjustment for vaccine group, age and baseline concentration - pooled variance); LL = lower limit, UL = upper limit

Template 31 Adjusted ratios of GMTs between groups (Control group divided by Co-Ad group) for anti-pneumococcal <X> antibody titres at one month post Prevenar 13 vaccine <PPS for immunogenicity, Exposed Set>

	Contro	ol			Co-Ad			Adjuste (Conti	d GMT ol / Co	
		95	% CI*			95%	CI*		95	% CI
N	Adjusted GMT	LL	UL	N	Adjusted GMT	LL	UL	Value	LL	UL

Co-Ad = Dose 1: Prevenar 13+ HZ/su, Dose 2: HZ/su

Control = Dose 1: Prevenar 13, Dose 2: HZ/su, Dose 3: HZ/su

Adjusted GMT = geometric mean antibody titre adjusted for vaccine group, age and baseline concentration N = number of subjects with both pre- and post-vaccination results available

95% CI* = 95% confidence interval for the adjusted GMT (Ancova model: adjustment for vaccine group, age and baseline concentration - pooled variance); LL = lower limit, UL = upper limit

95% CI = 95% confidence interval for the adjusted GMT ratio (Ancova model: adjustment for vaccine group, age and baseline concentration - pooled variance); LL = lower limit, UL = upper limit

Template 32 Mean Geometric Increase (MGI) of anti-gE antibody ELISA concentrations from baseline to one month post dose 2 of HZ/su vaccine <PPS for immunogenicity, Exposed Set>

								MGI		
									9	5% CI
Antibody	Group	N	Time point description	GMC	Time point description	GMC	Ratio order	Value	LL	UL
<antibody></antibody>	Co-Ad		PII(M3)		PRE		PII(M3)/PRE			
-	Control		PIII(M5)		PI(M2)		PIII(M5)/PI(M2)			

Co-Ad = Dose 1: Prevenar 13+ HZ/su, Dose 2: HZ/su

Control = Dose 1: Prevenar 13, Dose 2: HZ/su, Dose 3: HZ/su

N = **n**umber of subjects with available results at the two considered time points

GMC = geometric mean antibody concentration

95% CI = 95% confidence interval, LL = Lower Limit, UL = Upper Limit

PRE= Pre-vaccination at Day 1; PII(M3) = Post-vaccination dose 2 at Month 3 for Co-Ad group

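### The pneumococcal ANCOVA drops per-protocol subjects who have a Month 1 titre but no Day 1 MOPA titre, a small and avoidable loss of precision that the serum-priority rule can add to in Co-Ad only

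*Protocol*

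**What the plan says.** Protocol 10.7.2 (Family 3) and SAP 6.3.1.2 compare the Month 1 log titres of each serotype by ANCOVA, with the Day 1 log titre as a continuous covariate and group and age stratum as fixed effects. Four further provisions decide who enters that model.

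- SAP 12.1.2 does not replace missing immunogenicity measurements and states that "an analysis will exclude subjects with missing or non-evaluable measurements". Protocol 10.5.1 is looser: it excludes a subject from an analysis only when all measurements are missing. SAP section 9 does not list this as a change.
- SAP Template 31, the table of adjusted GMT ratios, defines "N = number of subjects with both pre- and post-vaccination results available". The same definition serves the per-protocol and the Exposed Set versions of the table.
- Elimination code 2100 in SAP 5.2.4 concerns post-vaccination results only. A missing Day 1 titre does not remove a subject from the per-protocol set.
- Protocol 5.8.4.1, Table 12, footnote 1 (Co-Ad) reads: "In case of inadequate samples from Visit Day 1, anti-gE testing (ELISA) will be prioritized over testing for pneumococcal serotype antibodies (MOPA". Table 13 (Control) has no such footnote.

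Protocol section 3 explains the difference between the tables. The Co-Ad Day 1 sample serves both assays. The Control Day 1 sample serves MOPA only, because the Control anti-gE baseline is drawn at Month 2.

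**The concern.** Taken together, these provisions let an observed primary-endpoint value be discarded because a covariate is missing. The subject stays in the per-protocol set but is absent from the confirmatory model, and the Exposed Set analysis does not bring the value back.

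Where serum is short and the priority rule is applied, this can happen only in Co-Ad. Control subjects with a lost or untestable Day 1 sample are dropped in the same way, but not through this rule.

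Precision is at stake in 13 sequential tests that must all succeed for the trial to be conclusive (Protocol 10.9). Neither document says how a missing baseline covariate is to be handled, and no template reports it as a loss. It would have to be inferred from the differing Ns in Templates 28 and 31.

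**Working it through.** **Inputs.** From Protocol 10.9: "All co-primary objectives will be evaluated using a one-sided Type I error of 2.5" per cent, with full alpha at each step. From Protocol 10.3 and Table 23: "For each pneumococcal serotype: non-inferiority limit = 0.301" on the log10 scale; "power under equal GMT"; 13 SDs from 0.644 (19A) to 1.094 (23F); 410 evaluable per group. Assumed, because the documents give neither: the share p of Co-Ad subjects without a Day 1 titre, and the share R² of Month 1 variance that the Day 1 titre explains.

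**Step 1: reproduce the stated power.** For each serotype SE = SD × √(1/n_Control + 1/n_Co-Ad), the noncentrality is 0.301/SE, and beta comes from the noncentral t. For 23F, SE = 1.094 × √(2/410) = 0.0764 and 0.301/0.0764 = 3.94, so beta = 2.41% against 2.398% in Table 23. The 13 betas sum to 9.05%, against 8.98% when the table's own values are added. Power is 91.0%, against the stated value of about 91%. Table 23 is a two-sample calculation and shows no covariate adjustment.

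**Step 2: remove Co-Ad subjects, with no gain from the covariate.** Control stays at 410.

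| Co-Ad loss p | Co-Ad n | Summed beta | Power |
|---|---|---|---|
| 0% | 410 | 9.0% | 91.0% |
| 1% | 406 | 9.3% | 90.7% |
| 5% | 390 | 10.4% | 89.6% |
| 10% | 369 | 12.1% | 87.9% |

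Power falls below 90% when 15 subjects are lost (3.7%).

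**Step 3: credit the covariate in the planned model.** If the Table 23 SDs are unadjusted, the residual SD is SD × √(1 − R²). If subjects without a baseline are kept, each carries roughly weight (1 − R²), so the effective Co-Ad n is 410(1 − p) + 410p(1 − R²). With p = 5% and R² = 0.1 this is 389.5 + 20.5 × 0.9 = 407.95.

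| Summed beta | R² = 0 | 0.1 | 0.2 | 0.3 |
|---|---|---|---|---|
| 5% lost, complete case | 10.4% | 5.7% | 2.7% | 1.0% |
| 5% without baseline, kept | 9.0% | 5.0% | 2.3% | 0.9% |
| 10% lost, complete case | 12.1% | 6.8% | 3.2% | 1.2% |
| 10% without baseline, kept | 9.0% | 5.0% | 2.4% | 0.9% |

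Keeping the subjects lowers beta in every column. With R² of 0.1 or more, however, the complete-case beta is also below the plan's 9%. The break-even is low. A 10% loss multiplies the variance by (1/410 + 1/369)/(2/410) = 1/0.947, so R² = 0.053 (a correlation of 0.23) offsets it. A correlation of 0.16 offsets a 5% loss.

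**Step 4: does filling in the covariate distort the ratio?** A simulation used 410 per arm, SD 1.094, R² of 0.1 or 0.3, and 5% or 10% of Co-Ad baselines missing at random and replaced by the both-arm mean. The estimated log10 difference stayed within 0.002 of the true zero, and coverage of the 95% interval was 94.6% to 95.4%.

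**The case against.** The strongest reply is that sample losses are already budgeted and the rule has a purpose. On the budget, Protocol 10.3 says "Assuming that about 10% of the subjects enrolled are non-evaluable (e.g. due to dropout, bad sample" and so on: 456 × 0.9 = 410, or 46 subjects per group. Loss within that allowance does not lower the power. This stands, with one qualification. The protocol glossary defines evaluable as being included in the per-protocol analysis, and these subjects are included. They can count towards the 410 and still be missing from the model.

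On the purpose, the Co-Ad Day 1 anti-gE value is needed for the vaccine response rate, which gates every later test, and it is the Co-Ad covariate in Family 2. This stands in full; the priority rule should not change.

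On frequency, the plan calls for at least 2.8 mL of serum per draw (Protocol 5.7.10.1) and gives no rate of inadequate samples. The footnote is a contingency, not evidence of expected loss. This also stands.

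Finally, baseline adjustment was clarified at the regulator's request in Amendment 2, so a change touches the confirmatory model for 13 tests. That is a reason to state the exception openly and to show the complete-case result beside it.

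**Conclusion.** The gap is real and minor. An observed Month 1 titre can be dropped from the confirmatory model, and any loss caused by the priority rule falls only on Co-Ad. The cost is precision: about 1.4 points of summed beta at 5% loss and 3.1 at 10% if the covariate explains nothing, and 0.8 and 1.7 points at R² = 0.1. The loss rates and R² are assumptions.

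A reader might infer more, but the documents do not support it.

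- **That the power claim fails.** Protocol 10.3 states: "The global power to meet all co-primary objectives with 410 evaluable subjects in Co-Ad and Control groups is approximately 91" per cent. A shortfall needs Co-Ad loss beyond the 10% allowance together with almost no gain from the covariate. Neither is shown.
- **That the comparison is biased.** If short serum at a pre-vaccination draw is unrelated to response, complete-case exclusion does not bias the ratio. The documents give no reason to expect a relation.
- **That the serum-priority rule is unjustified.** It protects the first test in the sequence.

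**What to change.** In SAP 6.3.1.2 and Template 31, include every per-protocol subject with a Month 1 titre for the serotype. Either replace a missing Day 1 log titre by the both-arm mean for that serotype, or fit a constrained longitudinal model with a common baseline mean. Keep the rule that outcomes are not imputed. Report the number of missing Day 1 titres by group, and show the complete-case ANCOVA as a sensitivity analysis.

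This needs a short SAP amendment and one extra table version, with no further samples or assays. The downside is a stated exception to the no-replacement rule, for a covariate only, in a model that a regulator has already commented on. Mean replacement also assumes that a missing baseline is unrelated to titre, which the sensitivity analysis helps a reader to judge.

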5.8.5. Immunological correlates of protection

No generally accepted immunological correlate of protection against HZ has been demonstrated so far for the gE antigen used in the HZ/su study vaccine.

No correlate of protection for pneumococcal conjugate vaccines for use in adults has been established.

The investigator is encouraged to share the immunological assay results for non-responders with the study subjects.

For the subjects identified as non-responders, it remains the responsibility of the investigator in charge of the subject's clinical management to determine the medical need for re-vaccination and to re-vaccinate the subjects as per local/regional practices.

CONFIDENTIAL

204487 (ZOSTER-059 PRI)
Protocol Amendment 2 Final**6. STUDY VACCINES AND ADMINISTRATION****6.1. Description of study vaccines**

The study vaccine to be used has been developed and manufactured by GSK Biologicals. The *Prevenar13* vaccine is marketed by Pfizer Inc..

The Quality Control Standards and Requirements for the study vaccine are described in separate Quality Assurance documents (e.g. release protocols, certificate of analysis) and the required approvals have been obtained.

The vaccines are labelled and packed according to applicable regulatory requirements.

Commercial vaccine(s) are assumed to comply with the specifications given in the manufacturer's Summary of Product Characteristics.

The characteristics of the study vaccines are presented in [Table 14](#).

Table 14 Study vaccines

Treatment name	Vaccine name	Formulation	Presentation	Volume to be administered	No. of doses
HZ/su	VZV gE	gE=50µg per 0.5 mL of reconstituted vaccine	Lyophilized pellet in a monodose vial	0.5 mL	2
	AS01 _B	MPL=50µg; QS21=50µg; Liposomes per 0.5 mL of reconstituted vaccine	Liquid in a monodose vial		
Prevenar13	Prevenar13	13 pneumococcal 13 polysaccharides (1, 3, 4, 5, 6A, 6B, 7F, 9V, 14, 18C, 19A, 19F, 23F), conjugated to cross-reactive material 197 carrier protein and adsorbed on aluminum phosphate (PS1=2.2µg CRM197; PS3=2.2µg CRM197; PS4=2.2µg CRM197; PS5=2.2µg CRM197; PS6A=2.2µg CRM197; PS6B=4.4µg CRM197; PS7F=2.2µg CRM197; PS9V=2.2µg CRM197; PS14=2.2µg CRM197; PS18C=2.2µg CRM197; PS19A=2.2µg CRM197; PS19F=2.2µg CRM197; PS23F=2.2µg CRM197; AIPO ₄ =125µg Al ₃₊)	Homogenous white suspension after shaking (in pre-filled syringe)	0.5 mL	1

HZ/su = Herpes Zoster subunit vaccine; VZV = Varicella Zoster Virus; gE = recombinant purified envelope glycoprotein E; µg = microgram; mL = milliliter; AS01_B = Adjuvant System AS01_B; MPL: 3-O-desacyl-4'-monophosphoryl lipid A. *QS21: Quillaja saponaria Molina, fraction 21 (Licensed by GSK from Antigenics Inc, a wholly owned subsidiary of Agenus Inc., a Delaware, USA corporation).

CONFIDENTIAL204487 (ZOSTER-059 PRI)
Protocol Amendment 2 Final**6.2. Storage and handling of study vaccine(s)**

The study vaccine(s) must be stored at the respective label storage temperature conditions in a safe and locked place. Access to the storage space should be limited to authorized study personnel. The storage conditions will be assessed during pre-study activities under the responsibility of the sponsor study contact. The storage temperature should be continuously monitored with calibrated (if not validated) temperature monitoring device(s) and recorded. Refer to the SPM for more details on storage of the study vaccine(s).

Temperature excursions must be reported in degree Celsius.

Any temperature excursion outside the range of 0.0 to +8.0°C (for +2 to +8°C/+36 to +46°F label storage condition) impacting investigational medicinal products (IMPs) must be reported in the appropriate (electronic) temperature excursion decision form ([e]TDF). The impacted IMPs must not be used and must be stored in quarantine at label temperature conditions until usage approval has been obtained from the sponsor.

In case of temperature excursion below +2.0°C down to 0.0°C impacting IMP(s) there is no need to report in (e)TDF, but adequate actions must be taken to restore the +2 to +8°C/+36 to +46°F label storage temperature conditions. The impacted IMP(s) may still be administered, but the site should avoid re-occurrence of such temperature excursion. Refer to the SPM for more details on actions to take.

Refer to the SPM for details and instructions on the temperature excursion reporting and usage decision process, packaging and accountability of the study vaccine(s).

